In the second version of the neurocognitive composite, the primary justifications for including the remaining neurocognitive measures are: 1) if significant missing data is seen on measure of processing speed, working memory, and fine motor skills, including a minor component of additional neurocognitive measures will ensure more reliably obtained data is contributing to the measurement of change, and 2) PTEN expresses in all of the cells of the body, the brains of PTEN patients showed widespread changes that included white matter abnormalities but also regional gray matter changes, and mouse models of PTEN loss have suggested that dendrite and synaptic dysfunction is also a consequence. Thus, it is reasonable to expect a range of neurocognitive functions might improve. Inclusion of other neurocognitive measures as the minority part of the index will ensure that improvements in other domains, such as expressive language, also have an opportunity to contribute to individual patient outcome measurements. Given that we do not yet know with certainty which neurocognitive functions are most likely to improve in this whole brain condition, allowing for possible improvement in other domains seems prudent.

Use of a neurocognitive composite score has several advantages. Assuming that everolimus treatment does not impair some functions while improving others (an unlikely scenario), a composite score is likely to be highly reliable, can be computed in all patients even if 1 or 2 measurements are missing or could not be completed, and has good domain coverage to capture possible variability across patients in the specific neurocognitive domains showing improvement. An example of the latter advantage, is if some individuals show improvements in processing speed while others show improvements in working memory. The neurocognitive composite would identify improvements in both of these sets of patients. As such, the neurocognitive composite may be more sensitive to change than any individual measure. Furthermore, a composite primary efficacy outcome will not require additional multiple comparison correction.

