In objective 2, we will examine whether the everolimus group will show more improvement, compared to the placebo group, on the main neurocognitive efficacy composite outcome. Randomization Group (everolimus versus placebo) differences on the neurocognitive composite will be analyzed using mixed effects (growth curve) modeling, fully utilizing repeated measurements collected at three points (Time: baseline, 3-month follow-up, and 6-month follow-up). A significant interaction between Time and Randomization Group, with the everolimus group showing a more favorable outcome trajectory, will support the primary efficacy hypothesis. Maximum likelihood estimation will be implemented in the Mplus program version 7.2 or above.

Mixed effects (growth curve) model analyses will be conducted following the intention-to-treat principle. Data points that are missing due to subject attrition will be handled assuming that data are missing at random (MAR) conditional on observed information, which is less restrictive than missing completely at random (MCAR) assumed in fixed effects analyses such as ANCOVA and regression analysis. In this procedure, all available cases including the ones with missing information will be included in the analyses. By including every subject who completed at least one assessment, we are not only more likely to conserve power, but also less likely to produce biased effect estimates. In mixed effects analyses, the slope of the outcome will be modeled as the key

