dependent variable predicted by randomization group. We will conduct the analysis with and without conditioning on relevant baseline covariates. The results of these longitudinal analyses can be easily converted to a cross-sectional group effect at each assessment time point to describe the magnitude and significance of group differences. Of particular interest is the group difference at end of treatment (6-month assessment). The mixed effects analyses will be repeated using a model where the baseline scores on each outcome are treated as a baseline covariate to control for (instead of as a part of) the repeated measures. This model can be useful if there is a considerable heterogeneity between before and after treatment processes. We will also analyze the data using conventional ANCOVA treating the end point neurocognitive composite as the dependent variable and controlling for the baseline neurocognitive composite. Further analyses will be conducted using the same analysis models but with transformed data (e.g., log transformation) to check the sensitivity of the results to deviation from outcome normality. Statistical significance of all main effects and interaction terms as well as cross-sectional group differences will be determined using a one-tailed Type 1 error rate of α =.05. The same analysis strategy will be employed for secondary efficacy outcomes and a false discovery rate correction will be implemented to control inflation of Type 1 error.

If the exploratory biosample objectives are pursued, we will explore whether baseline peripheral blood levels of PTEN-associated pathway molecules (PI3K/AKT, mTOR, MAPK protein levels) change with treatment and if changes in peripheral pathway molecules correlate with clinical improvement. To determine whether PTEN-associated pathway molecules change with treatment, we will use a similar mixed effect (growth curve) modeling approach to that described above for Secondary Objective with screening, 3-month, and 6-month pathway measurements as outcome measures. The Time by Randomization Group interaction will test whether the everolimus treatment group shows improvement/normalization of PTEN-pathway molecule levels relative to placebo. This component will be dependent on securing additional funds.

In analyzing the resting state EEG and AEP data we will focus on the following:

- 1. Baseline EEG gamma power
- 2. AEP N1 habituation

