Secondary Objective – Efficacy. For power estimation purposes, the variability in PTEN patients treated with an mTOR inhibitor is expected to be similar to the untreated sample. Preliminary data indicates that the measures which comprise the dominant portion of the neurocognitive composite index (processing speed working memory, and fine motor) are highly sensitive to the brain dysfunction seen in PTEN patients with ASD. The effect sizes are approximately 1 SD or larger. In a comparison between mTOR treated vs. untreated PTEN patients, an effect size of at least 0.65 SD would be of interest and represent clinically- meaningful improvement. For example, an effect size of at least 0.65 SD on cognitive measures would translate to a 10-point standard score improvement in the everolimus-treated group relative to placebo. An improvement of 10 or more points is outside the standard error of measurement for most cognitive measures and is typically considered a reliable change when disordered populations are re-tested.

A sample size of 40 (20 per arm) patients will permit detection of endpoint (6-month follow-up) differences of at least 0.80 SD at the 5% significance level (one-sided alpha = 0.05) with 80% power (1- β). Statistical power will be weaker (1- β =.65) if smaller cross-sectional differences are observed (0.65 SD). However, statistical power is very strong, even for smaller differences (Cohen's d≥.50 equivalent to ≥.50 SD difference) when the full repeated measures nature of the design is considered – baseline, 3-month follow-up, 6-month follow-up. Assuming even modest correlations between repeated measurements of outcome variables (r≥.30), power to detect clinically meaningful differences of .50 SD is very good (1- β =.83; one-sided α =.05). If the primary outcome measure (neurocognitive composite) meets nominal statistical significance in the expected direction (one-tailed p<.05) or a secondary outcome measure meets a more stringent false discovery rate-corrected

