significance level in the expected direction, these outcomes will be considered candidates for Phase III confirmatory trial evaluation. To determine if a secondary outcome meets the more stringent false discovery rate-corrected significance level, a Benjamini-Hochberg false discovery rate correction will be applied with adjustment for all secondary outcome measures. This adjustment involves sorting the list of obtained p-values in descending order. The smallest p-value is then compared to the most stringent alpha, the next smallest is compared to the next most stringent alpha, and so on. Only those secondary outcomes meeting FDR-corrected alpha level will be considered candidates for Phase III evaluation.

An interim analysis will be conducted after half the sample has been collected (10 patients in each arm) and will mainly focus on safety. Efficacy interim analysis may be under-powered, but will focus on whether the effects are in the expected direction and whether effect sizes (both the endpoint effect size and the interaction fully utilizing repeated measures) are approaching expected levels (at least Cohen's d≥.30). The goal of the interim analysis for efficacy will be to get a signal that will allow us to design more targeted trials in the future. As such, we will check for a signal in any domain and, if needed, include additional endpoints before the end of the study to expand the endpoint and optimize outcome.

Additional considerations. This is the first clinical trial in patients with PTEN mutations and ASD/DD. For this reason, and to facilitate recruitment, all types of PTEN mutations will be permitted within the randomized patients. However, post-hoc analyses will be completed to examine the existence of any differential effect of treatment based on the type of PTEN mutation (missense vs. other mutation types) or mutation location (exon number, location in 3-D PTEN structure).

18. Protocol Amendments or Changes in Study Conduct

Any change or addition (excluding administrative) to this protocol requires a written protocol amendment that must be reviewed by the central IRB at Boston Children's Hospital (Boston and Stanford only), Cleveland Clinic IRB the NIH, and Novartis as applicable. Amendments significantly affecting the safety of subjects, the scope of the investigation or the scientific quality of the study require additional approval by the IRB at each study center. A copy of the written approval of the IRB must be provided to Novartis.

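### The Phase III gate for the neurocognitive composite is not tied to one test, so its false-go rate is about 5% only if the Time by Group interaction alone is meant to open it

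*Combined protocol and SAP*

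**What the plan says.** Section 17.1 (Secondary Objective – Efficacy) holds the only decision rule for the composite: "If the primary outcome measure (neurocognitive composite) meets nominal statistical significance in the expected direction (one-tailed p<.05"). Outcomes that pass are dealt with as follows: "these outcomes will be considered candidates for Phase III confirmatory trial evaluation".

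Section 17, objective 2, says which result bears on the hypothesis: "A significant interaction between Time and Randomization Group, with the everolimus group showing a more favorable outcome trajectory, will support the primary efficacy hypothesis". It adds that "the slope of the outcome will be modeled as the key" dependent variable.

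The same part of section 17 then plans:

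- the main analysis with and without baseline covariates, which it does not list;
- group differences at each visit, with this emphasis: "Of particular interest is the group difference at end of treatment (6-month assessment");
- a second mixed model with the baseline score as a covariate;
- an ANCOVA of the end-point composite;
- repeats on transformed data.

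One threshold covers them: "Statistical significance of all main effects and interaction terms as well as cross-sectional group differences will be determined using a one-tailed" error rate of .05.

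Section 17.1 states power separately for the Month 6 difference and for the repeated-measures analysis. Its interim paragraph looks at the effect size for both. Section 7.9.3 defines two versions of the composite and says that "a composite primary efficacy outcome will not require additional multiple comparison correction".

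**The concern.** A rule that asks for significance, without saying in which analysis, can be met by more than one analysis. The slope and the Month 6 difference are different contrasts of the same data. The plan gives both prominence and the same alpha, and the gate sentence does not choose between them. If the choice is left until the results are known, a favourable result in either could be presented as passing.

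The remark in section 7.9.3 about multiplicity covers the pooling of several domains into one outcome. It does not cover several tests of that one outcome.

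At stake is how often an inactive treatment yields a Phase III candidate, and whether the conclusion was fixed in advance. The gap also reaches the secondary outcomes. Section 17 applies the same analysis strategy to them, and the Benjamini-Hochberg step in section 17.1 needs one p-value per outcome without saying which.

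**Working it through.** **Inputs.** From section 17.1: 20 per arm and a correlation between visits of at least .30. From section 17: three visits (baseline, Months 3 and 6) and one-tailed .05. Assumed: correlations of .3 to .9 (compound symmetry) and .5 to .9 (AR(1)); two covariates, each correlated .3 with the composite; complete, normal data.

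**1. The plan's own power figures.** For a two-group comparison at Month 6 the noncentrality is d × √(20/2), with 38 df and critical t = 1.686.

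- d = 0.80: 0.80 × 3.162 = 2.530, power 0.799 (plan: 80%).
- d = 0.65: 0.65 × 3.162 = 2.055, power 0.646 (plan: .65).

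Both are reproduced. The sample-size statement therefore rests on the Month 6 difference, not on the interaction.

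**2. Slope or Month 6 difference.** With equally spaced visits the slope is proportional to Month 6 minus baseline. Under compound symmetry its correlation with the Month 6 difference is (1−r)/√(2(1−r)) = √((1−r)/2). With no effect, P(either significant) = 0.05 + 0.05 − P(both).

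| r | correlation of tests | P(both) | P(either) |
|---|---|---|---|
| .3 | 0.592 | 0.0152 | 0.0848 |
| .5 | 0.500 | 0.0122 | 0.0878 |
| .7 | 0.387 | 0.0091 | 0.0909 |
| .9 | 0.224 | 0.0057 | 0.0943 |

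Simulation with t-tests (40,000 null trials per scenario, both correlation structures) gives 0.083 to 0.095.

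**3. Other readings of the gate, same simulation unless noted.**

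| What may open the gate | False-go rate |
|---|---|
| Interaction only, no covariates | 0.049–0.052 |
| Interaction, with or without covariates | 0.057–0.060 |
| Interaction, on either composite version (assumed correlation .80–.95 between versions; separate run of 200,000 trials) | 0.064–0.075 |
| Slope, Month 6 or ANCOVA | 0.085–0.100 |
| Those three plus Month 3 difference and baseline-adjusted post-baseline mean | 0.125–0.137 |
| Those five, each with and without covariates | 0.156–0.174 |

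Five independent tests would give 1 − 0.95⁵ = 0.226, so overlap between the tests already lowers these figures. Transformed-data repeats were not counted.

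**4. How often the choice matters.** Take a true 0.50 SD difference at Month 6, reached linearly. Power at Month 6 is Φ(0.50/√0.1 − 1.645) = Φ(−0.064) = 0.475. Power for the slope is Φ(0.50/√(0.2(1−r)) − 1.645), which is 0.379 at r = .3 and 0.893 at r = .85. The two tests disagree in 0.30 of trials at r = .3 and 0.48 at r = .85.

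**The case against.** The strongest reply is that section 17 already names the deciding test. The interaction is what supports the efficacy hypothesis, the slope is the key quantity, and the gate concerns the same outcome in the same part of the document. On that reading the false-go rate is about 5%. Much of the remaining wording also sounds supportive: the transformed-data runs are there to check sensitivity, the visit effects to describe magnitude and significance, and the baseline-covariate model for a particular circumstance. This stands. A reader might infer that the plan's false-go rate simply is 9% to 15% or more, but the documents state no rule that any test suffices.

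Second, section 17 derives the visit effects from the longitudinal model. If only the slope, and not the intercept, depends on group (one possible reading), the Month 3 and Month 6 effects are multiples of the slope effect and share its p-value. Slope or ANCOVA then gives about 0.05 to 0.075, and adding the baseline-adjusted mean gives about 0.075 to 0.10. This also stands as a limit on the higher figures. Against it, the Month 6 power calculation is that of a plain two-group comparison.

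Third, the study is exploratory, the threshold is called nominal, and passing creates only a candidate. That lowers the severity. Yet the plan corrects secondary outcomes for false discovery, so the gate is meant to limit false leads.

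Fourth, tests that disagree are not in themselves a defect: part of the disagreement reflects limited or unequal power. It shows only that the choice of test has consequences.

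**Conclusion.** The concern holds as a gap in the decision rule. The gate does not refer back to the interaction test, and the plan gives the Month 6 difference parallel standing in the analysis text, the power statement and the interim paragraph.

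The size depends on the reading: about 5% if one specified interaction test governs; about 6% to 7.5% if the covariate set or composite version is left open; about 8% to 9.5% if slope or Month 6 may qualify; about 13% to 17% if any listed test may. The last two ranges treat the visit differences as separate comparisons. All rest on assumed correlations and covariates and on complete, normal data.

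The documents do not support saying that a promised 5% decision error is breached, because they promise none beyond a nominal threshold. This is a cheap improvement.

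**What to change.** In section 17.1, state that the composite qualifies only if the Time by Group test of section 17 has one-tailed p<.05, in one stated covariate specification and on one composite version. If the sponsor prefers another lead contrast, name that one instead.

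Select the composite version by the missing-data rule of section 7.9.3, before unblinding. Section 7.6 breaks each participant's code around Month 6, so in practice this means before any composite result by arm is examined, including at the interim look. The rule also needs a single cut-off, since it now runs from nearly complete data to more than 20% missing with nothing between.

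In section 17, state that the per-visit differences, baseline-adjusted model, ANCOVA, other covariate version and transformed-data runs are supportive and cannot open the gate.

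This brings the rate to about 5%. It would be about 5.9% if the maximum-likelihood test uses a normal reference without a small-sample correction: P(t₃₈ > 1.645 × √(38/40)) = 0.0586.

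The cost is a few sentences and no new data or analyses. The small downside is that a favourable supportive analysis can no longer qualify the composite on its own.

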7.5 Randomization Procedure

Subjects will be randomized 1:1 to everolimus or placebo after meeting all eligibility criteria. A designated member of the research team will communicate to the participant that randomization has occurred and sufficient study drug will be dispensed to cover the interval until the next study visit. This is a double-blind study. The study design allows patient unblinding during the double-blind phase only in very precise circumstances (section 7.6.1).

Randomization data are to be kept strictly confidential until the time of unblinding at discontinuation or at the time of final analysis. These data will not be accessible to anyone involved in the conduct of the study with the exception of the unblinded physicians, the Medical Monitor, the Data Safety and Monitoring Committee (DSMC), and the Data Management Coordinating Center (DMCC). The DSMC will review safety data as outlined in section 15. The identity of treatment arms will be concealed by the use of study drugs (everolimus and matching placebo) that are identical in packaging, labeling, schedule of administration and in appearance.

Prior to Baseline (Visit 2), the investigator or his/her designee will log onto the data system to verify that the patient fulfills all eligibility criteria and randomize the patient to a treatment arm. The system will assign a randomization arm, as described in the 7904 Manual of Procedures. The pharmacy will be responsible for dispensing the active drug or placebo based on the procedures outlined in the 7904 Pharmacy Manual of Procedures. The randomization will be stratified by age. Age will be stratified by two levels. Level 1 will be participants aged 5-21 years old, and level 2 will be 22-45 year olds. Permuted block sizes of two and four will be used. At the conclusion of the 6-month double-blind phase, the blind will be broken immediately. Individuals on the active drug will exit the study, and those who were on placebo will be invited to join the open label phase.

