The Study Chair has primary oversight responsibility of this clinical trial. The appointed Data and Safety Monitoring Committee (DSMC) has oversight responsibility of the Data and Safety Monitoring Plan (DSMP) for this clinical trial. Each site's Principal Investigator and their research team (co-Investigators, research nurses, clinical trial coordinators, and data managers) are responsible for identifying adverse events. Aggregate report - detailed by severity, attribution (expected or unexpected), and relationship to the study drug/study procedures – will be available from the DMCC for site review. Adverse events will be reviewed by the research team at time of occurrence and reviewed at monthly team meetings.

The DSMC is an internally appointed group of individuals who will monitor and evaluate the safety of the proposed clinical trial. The DSMC's primary role is to ensure the safety of patients in the study. The DSMC will follow the NIH's published guidelines regarding its function and may provide input such as the recommendation to stop the trial for safety reasons. Due to the signal-seeking nature and the small sample size in this study, there is no formal efficacy interim analysis planned. However, the DSMC will review adverse events and serious adverse events and provide a report to the group bi-annually. The DSMC will include individuals familiar with everolimus administration and clinical trial design and will be comprised of [name]. (pediatric neurologist from Boston Children's Hospital), [name]. (pediatric neurologist at Stanford University, Chairperson), and [name]. (biostatistician from the University of North Carolina).

[name]. (Cincinnati Children's Hospital Medical Center) will be the independent medical review officer for this trial. He is an expert in the use of mTOR inhibitors in children and adults with TSC. [name] will review any adverse events/serious adverse events throughout and will also determine if unblinding and reporting to the FDA and DSMC is required. If [name] is unable to fulfill his duty at any point during the study, [name]. (Boston Children's Hospital) will serve as the back-up medical review officer until [name] returns to his duties.

16. Data Management and Coordinating Center and Database

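### Section 17.1 plans a half-way efficacy comparison by arm, with no named recipient and a licence to add endpoints, and this does not fit section 15, which says no formal efficacy interim is planned

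*Combined protocol and SAP*

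**What the plan says.** Section 17.1 (Power Estimation) states: "An interim analysis will be conducted after half the sample has been collected (10 patients in each arm) and will mainly focus on safety". The efficacy part then follows: "Efficacy interim analysis may be under-powered, but will focus on whether the effects are in the expected direction". It also asks whether effect sizes are near a benchmark of d = 0.30, for "both the endpoint effect size and the interaction fully utilizing repeated measures". Two uses are given. One is later research: "The goal of the interim analysis for efficacy will be to get a signal that will allow us to design more targeted trials". The other lies inside this trial: the team will look for a signal in any domain and may add endpoints before the study ends.

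Section 15 (DSMC) gives the small sample and signal-seeking purpose as the reason that "there is no formal efficacy interim analysis planned". The DSMC's stated task is to review adverse events and serious adverse events and to report twice a year.

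Section 7.5 restricts randomisation data: "These data will not be accessible to anyone involved in the conduct of the study with the exception of the unblinded physicians". Three further groups are also excepted: the DSMC, the DMCC and the Medical Monitor. The restriction runs until unblinding at discontinuation or until final analysis. Sections 4.3, 7.5 and 7.6 break each patient's blind at the end of the six months, and under 7.6 the site obtains the assignment before the Month 6 visit.

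**The concern.** A DSMC member or trial statistician cannot tell from sections 15 and 17.1 together whether a by-arm efficacy analysis is to be run at half-way. If it is run, both quantities compare the arms, so pooled blinded data cannot supply them. Someone must use the codes, and section 17.1 does not say who, or who may see the output. The protocol does build a firewall where it wants one: for dose changes driven by drug levels, section 6.2 names unblinded physicians and keeps the site team blind.

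Two things are at stake. First, a pooled estimate known to the team could colour what happens to patients still on blinded treatment: global and autism ratings, efforts at retention, and the reason recorded for stopping. That reason decides the primary endpoint, drop-out due to side effects. Second, an endpoint chosen because the first 20 patients showed a difference on it will be analysed at the end on data that include those same 20 patients. Its final estimate is then biased toward a benefit.

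**Working it through.** **Inputs.** From 17.1: 20 per arm at the end, 10 per arm at the look, benchmark d = 0.30, difference of interest 0.65 SD, one-sided alpha 0.05, repeated-measures correlation 0.30. From the synopsis: 40 randomised, two-year enrolment period. Assumptions: half the sample collected means 20 patients with Month 6 data, and accrual is even.

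**The plan's own figures.** For a two-sample t test with 20 per arm, the noncentrality is d × √(20/2) on 38 df. Power is 0.799 at 0.80 SD (stated 80%) and 0.646 at 0.65 SD (stated .65). The stated .83 at 0.50 SD is matched by a repeated-measures within-between F test with f = 0.25 and three times: λ = 0.25² × 40 × 3/(1 − 0.30) = 10.7 on 2 and 76 df, power 0.827.

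**The same formulas at 10 per arm.**
- Standard error of the unadjusted difference: √(2/10) = 0.447 SD. The 95% half-width is 2.101 × 0.447 = 0.94 SD, using t on 18 df.
- One-sided power is 0.53 at 0.80 SD and 0.40 at 0.65 SD.
- For the interaction, λ = 0.25² × 20 × 3/(1 − 0.30) = 5.36 on 2 and 36 df, and power falls from 0.83 to 0.50.

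**What the benchmark can tell.** Observed d is at least 0.30 when t on 18 df is at least 0.30 × √5 = 0.671, with noncentrality δ × √5 for a true effect δ.

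| True effect (SD) | Observed d ≥ 0.30 | Observed d ≤ 0 |
|---|---|---|
| 0 | 25% | 50% |
| 0.30 | 50% | 25% |
| 0.50 | 67% | 13% |
| 0.65 | 78% | 7% |

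A true effect of 0.65 SD therefore misses the benchmark 22% of the time.

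**Bias from choosing an endpoint on the signal.** Suppose a measure already collected is promoted because interim d is at least 0.30, and the drug has no effect on it. By the normal approximation, the expected interim value given selection is 0.447 × φ(0.671)/[1 − Φ(0.671)] = 0.447 × 0.3185/0.2512 = 0.57 SD. The second 20 patients average zero, so the final estimate averages about (0.57 + 0)/2 = 0.28 SD. A measure introduced afresh, with no data from the first 20, would not carry this bias.

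**Who is still under study.** Accrual of 40 in 24 months puts the 20th patient in at month 12 and at Month 6 in month 18. By then 40 × 18/24 = 30 are randomised. Of the 20 without Month 6 data, 10 are not yet randomised and 10 are on treatment. About 5 of those 10, enrolled between months 12 and 15, have passed Month 3.

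**The case against.** The strongest reply is that section 15 rules out only a formal efficacy interim. Section 17.1 puts safety first, admits low power, sets no boundary and no stopping rule, and belongs to a study described as mainly descriptive. That much is fair: the texts can be read as formal versus informal. But 17.1 fixes a time point, two measures, a benchmark and a resulting action, so the two sections still need reconciling.

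Several stronger readings are tempting and should not be made:
- **That section 7.5 is breached.** It governs randomisation codes, not aggregate results, and it lapses for each patient around Month 6. Sites will already know their own completers' arms, and one site expects at least half the sample (section 5). What the look adds is a pooled three-site estimate. Deleting it would not remove the knowledge that comes from rolling unblinding.
- **That investigators are certain to learn the effect.** No recipient is named, the first person plural is the protocol's ordinary voice, and the DMCC could run the analysis. That the team sees the result is an inference from the two stated uses.
- **That half the patients are still wholly unassessed.** They lack Month 6 data; some will have baseline or Month 3 data.
- **That type I error is inflated by repeated testing.** Two tests at one-sided 0.05 would give about 0.080, but 17.1 plans no interim significance claim.

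The route to bias is also limited. Independent evaluators of the global and autism ratings are blind to individual assignment (section 7.9.1), the composite is performance testing, and section 7.7.6 forbids recording withdrawal of consent when an adverse event or laboratory value was the cause. These points make bias less likely without excluding it. Added endpoints might need a reviewed amendment under section 18, but review does not undo selection on by-arm data.

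**Conclusion.** The point holds as a gap in the plan that should be closed. Sections 15 and 17.1 give different accounts of interim efficacy. Section 17.1 controls neither who sees the by-arm result nor the use of that result to change endpoints. The influence on later conduct is possible rather than shown, and its size cannot be derived from the documents. The selection bias is more definite: about 0.28 SD on average for a null measure picked at the benchmark, under the assumptions above. That is more than half of the 0.50 SD that 17.1 calls clinically meaningful.

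Against this, the look offers a half-width of 0.94 SD and a 25% chance of meeting its benchmark with no effect. Those two figures are for the unadjusted endpoint comparison. The interaction uses more data, but its power is only about 0.50 at the plan's own assumptions. Planning of later trials is better served by the final data. The timing assumes even accrual and that the 20 patients have completed Month 6.

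**What to change.** Bring 17.1 into line with section 15. Make the half-way analysis safety only, and delete both the efficacy look and the clause that allows endpoints to be added because of it.

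If an efficacy summary is kept, state that the DMCC prepares it for the closed DSMC session only; that no by-arm efficacy result goes to the study chair, site investigators, evaluators or sponsor staff before database lock; and that any endpoint added after the look is labelled exploratory. Section 15 and the DSMC charter should then list this review among the committee's tasks. This is the weaker choice, because section 15 describes the DSMC as internally appointed and two of its members come from recruiting institutions.

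The cost is wording in 17.1, and in section 15 and the charter if a summary stays. No patients, visits or sample size are affected. The team gives up an early and very noisy signal.
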